Objectives	
Primary Objectives:
 
1- To assess the 1-year PFS for patients with RPA class I and II disease treated with nivolumab and IMRT re-irradiation
 
Secondary Objectives:
 
1- Evaluate the OS of patients treated with re-irradiation and nivolumab 2- Evaluate patient QOL 3- Evaluate patterns of failure including rates of locoregional failure and distant failure 4- Identify and estimate the incidence rate of acute and late toxicities associated with combined re-irradiation and nivolumab followed by nivolumab
 
Exploratory Objectives:
 
 • To identify potential biomarkers related to clinical benefit to concurrent nivolumab and re-irradiation in patients with recurrent HNSCC.

SAEStudy Design	
This will be a phase II single arm study of IMRT re-irradiation in combination with nivolumab in the concurrent and maintenance setting. Patients with RPA class I and II based on the recursive partitioning analysis (RPA) classes reported by Ward et al (ASTRO 2016) will be enrolled. The allowable treatment approaches include IMRT. Based on this analysis, only patients with RPA classes I and II will be included; Class III patients will be excluded.
 
RT will be given as 60-66Gy in once daily fractions (2 Gy per fraction).
 
Nivolumab will be administered 2 weeks prior to the beginning of radiation therapy (1 dose at Week -2) and continue every 2 weeks during radiation (4 doses at Weeks 0, 2, 4, 6) for a total of 5 doses. Nivolumab will then be given every 4 weeks for 10 additional doses for a total of 15 doses of Nivolumab.

Number of Patients	
From the MIRI study, the 1-year PFS rate for class I and II combined was 43.8% (95% CI: 38.6 - 49.7%). Assuming a one sided alpha of 0.05 and an 85% power to detect an improvement in 1-yr PFS from 40% to 55% we estimate 46 patients will need to be accrued in 2.5 years and followed for an additional 2 years (estimated maximum total of 51 patients). Accounting for a 20% drop out rate, 62 patients will need to be consented.

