^h Tumor measurement: The scans may be performed within +/- 2 weeks of intended f/u times (wks 18, 30, 52, and 104). Additional scans should be obtained as clinically indicated if progression is suspected or symptoms warrant further investigation. No tumor measurements are required in the postoperative high risk setting where no gross disease is apparent.

ⁱ. For patients enrolled post salvage surgery, a CT of the Neck and Chest or a PET scan will be required as a baseline study prior to enrollment. The sites can use a simulation CT of the Neck and Chest for this purpose.

^j. Pregnancy test should be done in woman of childbearing age who are sexually active and may potentially be pregnant. Prior to study enrollment, women of childbearing potential (WOCBP) must be advised of the importance of avoiding pregnancy during trial participation and the potential risk factors for an unintentional pregnancy. In addition, men enrolled on this study should understand the risks to any sexual partner of childbearing potential and should practice an effective method of birth control. All WOCBP MUST have a negative pregnancy test within 7 days prior to first receiving Nivolumab. If the pregnancy test is positive, the patient must not receive investigational product and must not be enrolled in the study. In addition, all WOCBP should be instructed to contact the Investigator immediately if they suspect they might be pregnant (e.g., missed or late menstrual period) at any time during study participation. The Investigator must immediately notify BMS in the event of a confirmed pregnancy in a patient participating in the study.

^k. May allow a window of 7 days of delay for labs (CBC diff and Chemistries) and 7 days of delay for nivolumab infusion if nivolumab given every 4 weeks; may also allow a window of 3 days between History, PE and ECOG PS status and nivolumab infusion (regardless of the nivolumab schedule)

TABLE OF CONTENTS

PROTOCOL SYNOPSIS	3
SCHEMA	6
TREATMENT STUDY CALENDAR	7
TABLE OF CONTENTS	9
1. INTRODUCTION.....	11
1.1. MEDICAL BACKGROUND	11
1.1.1. Treatment of Recurrent Locoregionally Advanced Head and Neck Squamous Cell Carcinoma	11
1.1.2. The Role of Reirradiation in HNSCC	12
1.1.3. Immunotherapy in HNSCC.....	12
1.1.4. PD-1 and Nivolumab in HNSCC in the context of radiation therapy.....	13
2. RATIONALE, OBJECTIVES, AND BENEFIT-RISK ASSESSMENT.....	17
2.1. RATIONALE FOR PERFORMING THE TRIAL.....	17
2.2. TRIAL OBJECTIVES	17
2.2.1. Primary Objective.....	17

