2. RATIONALE, OBJECTIVES, AND BENEFIT-RISK ASSESSMENT

2.1. RATIONALE FOR PERFORMING THE TRIAL

This study seeks to investigate the potential benefit of the addition of adjuvant immunotherapy to IMRT based re-irradiation in RPA Class I and II patients with locoregional recurrent or second primary (RSP) head and neck squamous cancer. Our hypothesis is that nivolumab will lead to an improved disease control in this population at high risk of relapse which will translate into an improved 1 year progression-free survival (PFS) compared to the standard re-irradiation with IMRT. We also believe based on the recent PRO data presented at ESMO 2016, that nivolumab will preserve the quality of life in this heavily pre-treated patient population. Given these initial exciting results in patients with advanced head and neck squamous cancer, there is strong rationale for the addition of PD-1 inhibition to an IMRT re-irradiation backbone. This study explores this combination therapy against the standard IMRT re-irradiation with or without other systemic therapies used in the MIRI cohort.

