3. STUDY POPULATION

Number of Centers

Three sites will be involved.

Number of Participants

A total of 46 patients will need to be accrued in 2.5 years and followed for an additional 2 years (estimated maximum total of 51 patients). Accounting for a 20% drop out rate, 62 patients will need to be consented.

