7.3 END OF STUDY TREATMENT AND FOLLOW-UP PERIOD

Patients will be followed for 2 years from the initiation of treatment. The imaging studies will be performed at baseline and at week 18, 30, 52, and 104. Patients will continue to be followed thereafter by their treating physicians as per standard of care.

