8. STATISTICAL METHODS

Power Caclulation: From the MIRI study, the 1-year PFS rate for class I and II combined was 43.8% (95% CI: 38.6 - 49.7%) Assuming a one sided alpha of 0.05 and an 85% power to detect an improvement in 1-yr PFS from 40% to 55% we estimate 46 patients will need to be accrued in 2.5 years and followed for an additional 2 years (estimated maximum total of 51 patients). Accounting for a 20% drop out rate, 62 patients will need to be consented. The sample size calculation was based on assumptions of exponentially distributed death times and use of the exponential MLE test (42). Definition of clinical outcomes: PFS is defined as months from treatment started to evidenced progression or death and censored at last follow up without progression, and OS is defined as months from treatment started to death or censored at last follow up if alive.

Analysis plan: For primary objective, the 1-yr PFS and its 95% confidence interval will be estimated by Kaplan-Meier method for all patients, as well as in each stratum defined by p16 and RPA status, but this study is not powered at the level of subgroups. For the secondary objectives, Kaplan-Meier method will be used to assess 1-yr OS, PFS, or pattern of failure, and the incidence rate of acute and late toxicities will be described as frequency and percentage. QOL will be summarized by mean and standard deviation. For exploratory objectives, the predictability of related biomarkers (baseline PDL1 status, T-cell activation biomarkers, CD28 and TCF1 positivity on T lymphocytes and other biomarkers) to clinical

outcomes (OS and PFS) will be explored using both univariate and multivariable Cox proportional hazards model controlling for potential confounders.

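### Section 8 sizes the trial on a one-sided exponential MLE test of 40% vs 55%, but its analysis plan adopts no primary test or success rule, only a Kaplan-Meier 1-year PFS with a 95% CI

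*Combined protocol and SAP*

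**What the plan says.** The synopsis and section 8 give the same design statement: "Assuming a one sided alpha of 0.05 and an 85% power to detect an improvement in 1-yr PFS from 40% to 55" per cent. Section 3 repeats that "46 patients will need to be accrued in 2.5 years and followed for an additional 2 years". Section 8 then names the method behind the number: "The sample size calculation was based on assumptions of exponentially distributed death times and use of the exponential MLE test (42").

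The analysis-plan paragraph that follows says, for the primary objective, that "the 1-yr PFS and its 95% confidence interval will be estimated by Kaplan-Meier method for all patients", and also within p16 and RPA strata, for which no power is claimed. It mentions no test, p-value, reference rate or threshold. The primary objective (section 2.2.1) is to assess 1-year PFS. Section 2.1 goes further and hypothesises better disease control "which will translate into an improved 1 year progression-free survival (PFS) compared to the standard re-irradiation with IMRT". No other section supplies a primary test or a success rule.

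On follow-up, section 7.3 says "Patients will be followed for 2 years from the initiation of treatment" and then "Patients will continue to be followed thereafter by their treating physicians as per standard of care". Footnote h of the study calendar says "The scans may be performed within +/- 2 weeks of intended f/u times (wks 18, 30, 52, and 104").

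**The concern.** A single-arm trial with a stated null, alternative, alpha and power is meant to end in a decision. Here the power paragraph rests on one method and the analysis plan on another. The exponential MLE test uses every PFS event over the whole follow-up. The Kaplan-Meier estimate at 1 year uses only what happened in the first year. A two-sided 95% interval also does not match a one-sided 0.05 test.

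Several rules are compatible with the text: the MLE test, a 95% interval that excludes 40%, or a one-sided test of the 1-year rate. They can give different answers on the same data. With no rule fixed in advance, a reader of the results cannot tell whether the one applied was chosen beforehand, or whether the 85% power belongs to it.

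**Working it through.** **Inputs (section 8).** Null 40%, alternative 55%, one-sided alpha 0.05, power 85%, accrual 2.5 years plus 2 years, 46 patients (maximum 51). Assumptions: exponential PFS, uniform accrual, no losses. The sizing sentence speaks of death times; because the rates are PFS rates, I apply it to PFS events.

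**Step 1: reproduce the 46.**
- Hazards: -ln 0.40 = 0.9163 and -ln 0.55 = 0.5978 per year. Ratio 0.652; ln(0.652) = -0.427.
- Events needed on the log-hazard scale: (1.645 + 1.036)² / 0.427² = 39.4.
- Chance of an event under 55%, with hazard λ = 0.5978: 1 - [exp(-2λ) - exp(-4.5λ)] / (2.5λ) = 0.843.
- N = 39.4 / 0.843 = 46.8. The cube-root form gives 45.3, which rounds up to 46; by that form power is 84.8% at 45 and 85.5% at 46.
- Power at 46 on the log scale: expected events 46 × 0.843 = 38.8; √38.8 × 0.427 - 1.645 = 1.01, so 84.5%.

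Simulation (100,000 trials per cell, n = 46, follow-up to 4.5 years):

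| Form of the MLE test | Error at 40% | Power at 55% |
|---|---|---|
| Likelihood ratio | 4.6% | 86.1% |
| Log hazard | 4.0% | 84.5% |
| Cube root, SE at the estimate | 4.7% | 86.2% |
| Cube root, null SE | 3.3% | 82.7% |
| Raw-hazard Wald | 6.0% | 88.4% |

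The stated 46 and 85% are right for the named test.

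**Step 2: what the written analysis would deliver if it decided.** With no censoring before 1 year, the Kaplan-Meier estimate is a binomial proportion. Neither rule below is in the protocol.

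| Hypothetical rule | n | Success needs | Error at 40% | Power at 55% |
|---|---|---|---|---|
| 95% CI excludes 40% | 46 | 26/46 | 1.7% | 47.8% |
| 95% CI excludes 40% | 51 | 28/51 | 2.2% | 56.3% |
| One-sided 0.05 test | 46 | 25/46 | 3.4% | 59.5% |
| One-sided 0.05 test | 51 | 27/51 | 4.2% | 67.0% |

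A cut-off of 24/46 would have 6.4% error. At a true PFS of 55% and n = 46, the one-sided Kaplan-Meier test and the MLE forms that hold 5% disagree in about 27-29% of trials, nearly always because only the MLE test succeeds.

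**Step 3: reliance on a constant hazard.** The documents give one PFS time point for classes I and II, so they neither support nor refute it. As an assumption of mine, take Weibull PFS with exactly 40% at 1 year and use the likelihood-ratio form at n = 46 with follow-up to 4.5 years. Shape 0.8 gives 17.6% actual error; shape 1.2 gives 0.7%.

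**Step 4: follow-up (conditional).** If PFS follow-up ended at 2 years per patient, the event chance under 55% would be 1 - 0.55² = 0.698, or 32.1 events at n = 46. The log-scale formula gives √32.1 × 0.427 - 1.645 = 0.77, so 78%. Simulated power is 79.7% (log) and 81.7% (likelihood ratio), and 77.1% for the conservative null-SE cube-root form.

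**The case against.** The gap is narrow. The null, alternative, alpha and a named test stand one paragraph above the analysis plan. The exponential MLE test is the only test the protocol names, so it is probably meant to decide. An estimate with an interval also answers an objective worded as assessing 1-year PFS. I accept the likely intent. Still, the sentence describes how the number was derived, not how the data will be judged, and the only primary analysis written is a different method.

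Three stronger readings should be resisted.
- A reader might infer that the trial is underpowered. The documents do not support that: 46 is correct for the named test, and the 48% and 60% belong to rules the protocol does not state.
- A reader might infer that only the MLE test gives 85%. That is not so: a one-sample log-rank test against the same exponential 40% null has about 85% power at 46 with 4.0% error. The power belongs to tests that use the whole follow-up under that model.
- A reader might infer that PFS follow-up stops at 2 years and that power has fallen. Section 7.3 adds standard-of-care follow-up, the 2 years in sections 3.1.4 and 7.5 may limit survival only, and section 8 censors PFS at last follow-up. The texts need reconciling; the cap is not established.

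The choice among MLE forms is also not settled by the documents. The likelihood-ratio form is one acceptable option, and the lowest power figures come from one conservative variant.

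**Conclusion.** The omission holds with high confidence: section 8 powers the trial on a one-sided 0.05 exponential MLE test against 40%, and the analysis plan does not adopt that test or any success rule. The sizing is right, at about 84-86% power for 46 patients with follow-up to 4.5 years. What is missing is the link from that calculation to the decision. It is more than a formality, because judging success from the planned Kaplan-Meier result would give about 48% or 60% power at 46, and 56% or 67% at 51, depending on the rule.

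These figures assume exponential PFS, uniform accrual and no losses; censoring before 1 year would lower the Kaplan-Meier power further. The follow-up point is separate and conditional: only if PFS is not followed beyond 2 years does MLE power at 46 become about 80-82%, or about 77% for the null-SE cube-root form. This should be fixed before outcome data are examined.

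**What to change.** Add to the section 8 analysis plan, for example:

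> Primary test: one-sided exponential MLE test of 1-year PFS 40% at the 0.05 level, in the form used for the sample size [name it]. The trial is positive if p < 0.05. The Kaplan-Meier 1-year PFS with its confidence interval is reported alongside, because the test relies on a constant hazard.

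The form should have actual error near or below 5%. The log, likelihood-ratio and cube-root forms do; the raw-hazard Wald form, at about 6%, does not.

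Alternatively, if the Kaplan-Meier 1-year rate is to decide, state that rule with the matching one-sided level (90% interval) and restate power as about 60% at 46 and 67% at 51. Name the interval's scale: at 46 patients a log-log 90% interval needs 25/46, while a plain one admits 24/46 and its 6.4% error.

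Separately, state whether PFS is followed beyond 2 years per patient, and reconcile section 8 with sections 3.1.4, 7.3 and 7.5 and the scan calendar. If it is not, restate the MLE power as above. Use one power statement in the synopsis and section 8.

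Cost: protocol wording only, with no extra patients. The downside is that the stated power may become less favourable.

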1.1.2. The Role of Reirradiation in HNSCC

With the advent of advanced radiation planning techniques (e.g. IMRT, VMAT), the feasibility and safety of re-irradiation has greatly improved, as has the therapeutic ratio. A recent multi-institutional collaborative study (named MIRI) of over 400 patients treated with IMRT based re-irradiation at 8 institutions, found that the overall acute grade 4-5 toxicity was only 5.6%, and grades ≥ 3 late toxicity was only 13% at two years. Overall, the 2-yr (40%) and 5-yr (22%) survival rates compared favorably to historical data (21). Most importantly, a recursive portioning analysis identified three distinct subgroups of patients with 2-yr OS of 62%, 40% and 17%, respectively, for classes I, II and III (21). This finding underscores the suboptimal outcomes in class III patients (e.g. <2 years between the first and planned second RT courses and in patients with pre-re-irradiation gastrostomy or tracheostomy tubes) for whom prolonged conventionally fractionated IMRT based re-irradiation may not be of benefit. On the other hand, IMRT based re-irradiation produces better results in patients with class I (e.g. >2 yrs between the first and planned second RT courses, and for patients managed with initial resection followed by post-op re-irradiation) and class II disease (e.g. all others), the associated 2 yr overall survival of 50% underscores the need for further improvements to this treatment paradigm in these patients. In a subset analysis of the MIRI collaborative study, the addition of systemic therapy (platinum or cetuximab based) did not appear to positively impact outcomes.

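### The 46 patients and 85% power come from a constant-hazard exponential test, but the planned analysis is a Kaplan-Meier 1-year PFS, for which a one-sided 5% test has about 60–67% power

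*Combined protocol and SAP*

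**What the plan says.** The design paragraph of Section 8 sets out the target as "Assuming a one sided alpha of 0.05 and an 85% power to detect an improvement in 1-yr PFS from 40% to 55"%, and concludes that "46 patients will need to be accrued in 2.5 years and followed for an additional 2 years", with an estimated maximum of 51. It states that the calculation rests on "assumptions of exponentially distributed death times and use of the exponential MLE test".

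The analysis plan in the same section uses a different method: "the 1-yr PFS and its 95% confidence interval will be estimated by Kaplan-Meier method for all patients". It names no hypothesis test, critical value or success rule.

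The only PFS figure for the reference population is a single MIRI value at 1 year, 43.8% in classes I and II combined. Section 1.1.2 gives MIRI survival at two time points, but for overall survival in the whole cohort: "Overall, the 2-yr (40%) and 5-yr (22%) survival rates compared favorably to historical data". It also gives "2-yr OS of 62%, 40% and 17%, respectively, for classes I, II and III". Class III is excluded from this trial (Section 3.1.2).

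On follow-up, Section 8 adds 2 years to a 2.5-year accrual period. Sections 7.3 and 7.5 follow each patient for 2 years, counted from the start of treatment and from the start of radiation respectively.

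**The concern.** An exponential test estimates one hazard as events divided by person-time, pooled over all follow-up. It gains precision for the 1-year rate by using events and time after year 1. A Kaplan-Meier estimate at 1 year takes nothing from later follow-up and assumes no shape. Power computed for the first does not carry over to the second.

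The extra precision is bought with the constant-hazard assumption. If the hazard falls over time, late low-risk person-time lowers the pooled hazard and raises the fitted 1-year PFS, so a treatment at exactly 40% would look better than it is. In a single-arm trial meant to show improvement over a historical rate, the plan therefore leaves one of two quantities in doubt. If the 1-year rate decides, the power is overstated. If the exponential test decides, the error rate depends on an unverified shape.

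**Working it through.** **1. Reproducing 46.** Inputs from Section 8: one-sided alpha 0.05, power 0.85, 1-year PFS 40% against 55%, accrual A = 2.5 years, further follow-up F = 2 years.
- Hazards: λ0 = −ln 0.40 = 0.916 and λ1 = −ln 0.55 = 0.598 per year, ratio 0.652.
- Event probability with uniform accrual: p = 1 − [exp(−λF) − exp(−λ(A+F))]/(Aλ), giving 0.937 under the null and 0.843 under the alternative.
- On the cube-root hazard scale, N = {[1.645·λ0^(1/3)/(3√p0) + 1.036·λ1^(1/3)/(3√p1)] / [λ0^(1/3) − λ1^(1/3)]}² = [(1.645×0.3344 + 1.036×0.3058)/(0.9713 − 0.8424)]² = 45.3, so **46**.
- The log-hazard scale gives 43.9, so 44.

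The stated size is therefore correct for the exponential test, with patients followed for 2 to 4.5 years.

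**2. Power of a test of the 1-year rate.** Assume no censoring before 1 year, so that the Kaplan-Meier estimate is a simple proportion x/n. The one-sided 95% lower log-log limit is S^exp(1.645·se), with se = √[(1−S)/(nS)]/|ln S|.
- n = 46: x = 24 gives a limit of 39.5% and x = 25 gives 41.6%, so at least 25 are needed.
- n = 51: x = 26 gives 39.0% and x = 27 gives 40.9%, so at least 27 are needed.

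The exact binomial test has the same thresholds.

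| n | Needed | P(success) at 40% | Power at 55% |
|---|---|---|---|
| 46 | 25 | 3.4% | 59.5% |
| 51 | 27 | 4.2% | 67.0% |

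By normal approximation, 85% power needs [(1.645√0.24 + 1.036√0.2475)/0.15]² = 77.6, so about 78 patients. Exact power at 78 is about 84%.

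If success were instead read from the planned two-sided 95% interval, z becomes 1.96. At n = 46, x = 25 gives a lower limit of 39.0% and x = 26 gives 41.1%, so 26 are needed. The binomial probability of 26 or more at 55% is 47.8%.

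**3. Is a constant hazard supported?** The MIRI overall survival figures are 40% at 2 years and 22% at 5 years.
- Constant hazard through 40% at 2 years: 0.40^2.5 = 10.1% at 5 years, against 22%.
- Average hazard: −ln 0.40/2 = 0.458 per year in years 0–2, and −ln(0.22/0.40)/3 = 0.199 per year in years 2–5, a ratio of 0.435.
- Equivalent Weibull shape: ln(ln 0.22/ln 0.40)/ln 2.5 = 0.548.
- Mixing RPA classes does not explain it. With exponential times within class and 40% overall at 2 years, the highest 5-year figure comes from classes I and III alone: 0.511×0.62^2.5 + 0.489×0.17^2.5 = 16.1%.

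**4. Sensitivity of the exponential test.** Simulated false-success rate at nominal 5%, n = 46, true 1-year PFS exactly 40% (log / cube-root scale). Every PFS shape is an assumption.

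| Assumed PFS hazard | Follow-up 2–4.5 years | Follow-up 2 years each |
|---|---|---|
| Weibull shape 0.548 | 44.5% / 46.6% | 17.3% / 19.1% |
| Weibull shape 0.8 | 16.1% / 17.7% | 9.0% / 10.2% |
| Weibull shape 0.9 | 8.8% / 9.9% | 6.4% / 7.4% |
| Constant to 2 years, then ×0.435 | 14.1% / 15.7% | 4.0% / 4.8% |
| Class I/II mixture, exponential within class | 7.6% / 8.7% | 5.6% / 6.6% |

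Under a constant hazard with follow-up of 2–4.5 years the rates are 4.0% / 4.7%, as intended.

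**The case against.** The strongest reply is that the exponential test appears only in the sample-size statement. The analysis plan is Kaplan-Meier, which needs no constant hazard, and no sentence says the exponential test will decide success. That is correct. A reader might infer from step 4 that the trial will declare false success far more often than 5%. The documents do not support this, because they do not plan that analysis.

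A reader might also infer that the protocol's own figures contradict a constant PFS hazard. They do not. The 40% and 22% are overall survival in a cohort that includes class III, and a single PFS value at 1 year cannot show a shape. The two survival points show a lower average hazard after year 2 but say nothing about shape before it. If the fall comes only after year 2 and each patient is followed for 2 years, the test holds about 5%. The direction is not fixed either: a rising hazard (shape 1.15) brings the error down to about 2% with the 2-year cap. Shape 0.548 is also an extreme for this trial. With 40% at 1 year it puts 40% of patients progressed or dead by week 18, the first scheduled disease assessment, although entry requires a life expectancy above 6 months.

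These points limit the error-rate argument to a conditional sensitivity result. They leave the power result untouched, since it needs no assumption about shape. The fact that the analysis is Kaplan-Meier is the reason the stated 85% does not apply to it.

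**Conclusion.** The concern holds as a mismatch between the test used for sizing and the planned analysis. The 85% at 46 patients is right for the exponential test and wrong for a one-sided 5% test of the 1-year rate, where power is about 60% at 46 and 67% at 51. This assumes no censoring before 1 year; censoring would be expected to lower it further.

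The constant-hazard assumption is unsupported, but it has not been shown to be false for PFS in classes I and II. If the exponential test were used for inference, its error may exceed 5%: roughly 5% to 20% with 2 years of follow-up per patient, and up to about 45% with 2 to 4.5 years. The upper ends require PFS in classes I and II to follow the shape of overall survival in all classes. The statement that the test will not hold its 5% error goes beyond the documents.

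**What to change.** In Section 8:
- Name the primary test: Kaplan-Meier 1-year PFS against 40%, log-log, one-sided 5%. Success means that the one-sided 95% lower limit lies above 40%. Say that this corresponds to a two-sided 90% interval, so that the reported 95% interval is not taken as the decision rule.
- State that the exponential MLE test will not be used for inference.
- Replace 85% with about 60% at 46 and 67% at 51 patients, and carry the change into the synopsis.
- Reconcile the follow-up assumed in the calculation with Sections 7.3 and 7.5.

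The cost is wording and a visibly lower stated power. No new data are needed. Keeping 85% would mean about 78 evaluable patients, which is a resourcing decision for the sponsor.

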Test	Pre-therapy (Day -30 to -1 before Nivolumab)	Every 2 weeks during each Nivo cycle before and during radiation	Every 4 weeks during each Nivo cycle for maintenance phase ^k	Wk 18 and 30 disease assessment ^a	Wk 52 (1yr after start of radiation) or at the time of disease progression	Wk 104 (yr 2 after start of radiation) or at the time of disease progression
History and physical ^b	X	X ^k	X ^k	X ^k	X	X
Weight and ECOG PS	X	X ^k	X	X	X	X
Tumor measurement (if applicable)	X			X	X	X
CBC and diff ^c	X	X	X		X	X
Chemistries (Na, Cl, CO2, K, BUN, Creatinine, Ca, Phos)	X	X ^k	X ^k		X	X
Liver function panel ^d	X	X	X		X	X
PT, PTT, INR	X				X	X
TSH	X		X		X	X
Tissue for research purposes - fresh biopsy (paraffin embedded if fresh tissue not available) ^{e, f}	X				X	
Blood for research purposes	X	X		X	X	X
Toxicity assessment ^g	X	X		X	X	X
QOL assessment	X	Wk 6 at completion of radiation		X	X	X
Radiology: 1. PET/CT or 2. CT- or MRI-neck AND CT-chest, CT-abdomen for tumor measurements ^h	X ⁱ			X	X	X

Serum B-HCG ^j	X						
--------------------------	---	--	--	--	--	--	--

^a. Disease assessments may be done +/- 2 weeks of specified time in protocol to allow for scheduling and/or transportation needs of the patient

^b. If Nivolumab or radiation has to be permanently discontinued due to side effects, H&P must be done 4 and 8 weeks after treatment discontinuation.

^c. CBC and diff include WBC, ANC, HCT, HGB, PLT, % lymphocytes, % monocytes, % neutrophils.

^d. Liver function panel includes Alk Phos, total bilirubin, SGOT (AST), SGPT (ALT), total protein.

^e. Fresh biopsy will be obtained before the first treatment when feasible. If tissue is not obtained, it is not considered a protocol deviation.

^f. Participating sites could have restricted number of research specimens (up to 6 draws per patient) depending on financial constraints;

^g. Toxicity assessment: Common Toxicity Criteria (CTC) version 4.03 will be used. All toxicity grades (including grade 1) should be captured on the case report forms. All toxicities that occurred during treatment and until 100 days following completion of therapy should be followed until resolution.

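### The start of the PFS clock is ambiguous and no rule ties the week-52 scan to the 1-year estimate, so the Kaplan-Meier 1-year PFS can be biased upward

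*Combined protocol and SAP*

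**What the plan says.** Section 8 defines the endpoint: "PFS is defined as months from treatment started to evidenced progression or death and censored at last follow up without progression". OS is counted from the same start. For the primary objective, "the 1-yr PFS and its 95% confidence interval will be estimated by Kaplan-Meier method for all patients". The sample size rests on "exponentially distributed death times and use of the exponential MLE test".

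The documents use two origins. Sections 4.1 and 4.3.1 place the first nivolumab dose two weeks before the first radiation fraction, and section 4.3.1 allows +/- 5 days. The calendar's baseline column is also set relative to nivolumab. Section 7.3 follows patients for two years from initiation of treatment, whereas sections 3.1.4 and 7.5 count the two years from radiation.

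The Treatment Study Calendar heads the 1-year column "Wk 52 (1yr after start of radiation) or at the time of disease progression". Its footnote h adds: "The scans may be performed within +/- 2 weeks of intended f/u times (wks 18, 30, 52, and 104". The preceding scheduled scan is therefore at week 30. The same footnote provides that "Additional scans should be obtained as clinically indicated if progression is suspected or symptoms warrant further investigation". History and physical are scheduled "Every 4 weeks during each Nivo cycle for maintenance phase". After permanent discontinuation for side effects, footnote b requires that "H&P must be done 4 and 8 weeks after treatment discontinuation".

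Section 8 contains no landmark window, no rule on how the week-52 scan enters the 1-year estimate, and no interval-censored method.

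**The concern.** Progression is dated when it is evidenced. A progression that arises without symptoms after the week-30 scan and is first seen at the week-52 scan takes the date of that scan. If the date is later than 12 months from time zero, the patient counts as progression-free at 1 year although the disease progressed within the year.

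On the literal clock this happens even when the scan is done exactly on schedule. The error runs in one direction only, and the trial is uncontrolled, with its primary result a single landmark percentage set against a historical rate. If time zero and the dating rule are not fixed in advance, both could also be chosen after the data are seen.

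**Working it through.** **The plan's own figure.** The hazards are -ln 0.40 = 0.916 and -ln 0.55 = 0.598 per year, a ratio of 0.652. Events needed are ((1.645 + 1.036)/ln 0.652)² = 39.4. With 2.5 years of uniform accrual and 2 further years, the event probability under the alternative is 0.843, so N = 39.4/0.843 = 46.8. Power at the stated 46 is 84.5%. The stated sample size reproduces, and this point does not touch it.

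**Share of the scan window after 12 months (365.25 days).**
- Radiation clock: 364 +/- 14 gives days 350 to 378. Share after: (378 - 365.25)/28 = 45.5% (46.4% with a 365-day year).
- First-nivolumab clock, 14-day lead: days 364 to 392. Share after: (392 - 365.25)/28 = 95.5% (96.4% with a 365-day year). Averaged evenly over leads of 9 to 19 days it is 93.0%.

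These are shares of the permitted window. They are shares of scans only if scans spread evenly over it.

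**Size of the bias.** Let f be the share of events found only on scheduled scans. This is an assumption; the documents give no figure. All other events keep their true dates. Take a constant hazard and a true 1-year PFS of 40%, so S(t) = 0.40^(t/365.25).

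*Every scan on time.*
- Nivolumab clock: scans fall on days 224 (week 30) and 378 (week 52). Silent events between day 224 and 12 months are all missed, so the estimate is 0.40 + f × [S(224) - 0.40] = 0.40 + f × (0.570 - 0.400) = 0.40 + 0.170f.
- Radiation clock: the scan on day 364 catches nearly all of them, so the estimate is 0.40 + f × [S(364) - 0.40] = 0.40 + 0.001f.

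*Scans spread evenly over +/- 14 days.*
- Nivolumab clock, lead 9 to 19 days: about 0.40 + f × 0.930 × 0.170 = 0.40 + 0.158f.
- Radiation clock: late scans miss events since week 30, and early scans miss the few events between scan and 12 months. The estimate is about 0.40 + f × [0.455 × (0.590 - 0.400) + 0.545 × (0.408 - 0.400)] = 0.40 + 0.091f.

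Simulation with 1,000,000 event times agrees with these approximations to about 0.1 point. The spread rows below are simulated.

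| True 40% reads, at f = | 10% | 20% | 30% | 50% |
|---|---|---|---|---|
| Nivolumab clock, on-time scans | 41.7 | 43.4 | 45.1 | 48.5 |
| Nivolumab clock, spread | 41.6 | 43.2 | 44.7 | 47.9 |
| Radiation clock, on-time scans | 40.0 | 40.0 | 40.0 | 40.1 |
| Radiation clock, spread | 40.9 | 41.9 | 42.8 | 44.6 |

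On the nivolumab clock the time origin causes the bias; spreading the scans slightly reduces it. On the radiation clock the window causes all but a negligible part of it. Of progressions first found on the week-52 scan, about 93 to 94% (nivolumab) and 47% (radiation) are dated after 12 months when scans spread evenly.

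In patients, the spread rows amount to 0.7 / 1.5 / 2.2 / 3.6 of 46 (nivolumab) and 0.4 / 0.9 / 1.3 / 2.1 of 46 (radiation). The binomial standard error is √(0.4 × 0.6/46) = 7.2 points.

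**A milder assumption.** Suppose every progression is found after a mean 4-week delay, or at the next scan if sooner, with 0 to 30% of events being deaths. Then 40% reads 41.9 to 42.8% (nivolumab) or 41.2 to 41.8% (radiation).

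**The case against.** The start of treatment is a named event, and nivolumab is plainly the first protocol treatment. The follow-up sections say how long patients are followed and do not define the PFS origin. The calendar labels week 52 as 1 year. This stands so far as to make the origin ambiguous, not undefined. It does not help the estimate, because the literal reading is the one with the larger bias.

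Detection between scans is better than the scan schedule suggests. Ten 4-weekly maintenance doses after radiation run to roughly week 46, with an examination at each, and suspicion prompts a scan. This stands: it lowers f, perhaps considerably. It does not bring f to zero, since examinations may miss silent progression, and patients who stop for side effects have only two further examinations specified before the scheduled assessments.

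Dating progression when found is ordinary Kaplan-Meier practice, and the historical cohort may carry the same bias. This also stands. That cohort's time origin and scan schedule are not given, so the net effect against the benchmark cannot be computed.

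The only test named, the exponential MLE, hardly depends on the clock: at f = 20 / 30 / 50% a true 40% reads about 41.9 / 42.9 / 44.6% on either. The choice of origin therefore matters for the Kaplan-Meier landmark, which is the primary estimate.

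Finally, a reader might subtract the radiation-clock reading from the nivolumab-clock reading, call the difference the effect of the origin, and call the remainder the effect of the scan window. The on-time rows show that this split is wrong on both clocks.

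**Conclusion.** The point holds and should be fixed. Time zero is ambiguous, and section 8 does not say how the week-52 scan enters the 1-year PFS. On the first-nivolumab clock the estimate is biased upward whenever some progressions are found only on scheduled scans, even with perfect scheduling. On the radiation clock it can be biased upward if scans spread over the permitted window.

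The size rests on three assumptions: a constant hazard, scans spread evenly over the window, and a scan-only share that the documents do not give. At shares of 10 to 20% the shift is 1.6 to 3.2 points (nivolumab) or 0.9 to 1.9 points (radiation). At 50% it is 7.9 or 4.6 points. All but the 7.9 lie below the 7.2-point standard error.

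A reader might infer that the trial could declare success falsely, because with no event dated between scans a true 40% reads about 56% on the nivolumab clock, above the 55% target. The documents do not support this: they provide for prompted scans and frequent visits, deaths keep their own dates, and any matching bias in the benchmark is unknown. No effect on the decision is claimed.

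**What to change.** In section 8:

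1. Name time zero for PFS and OS, and reconcile the follow-up origins in sections 3.1.4, 7.3 and 7.5 with it. The first nivolumab dose is the natural choice.
2. State that the 1-year PFS includes progressions found on the week-52 scan. Assign a progression first found on a scheduled scan to the nominal scan time, or to the date of death if earlier, so that PFS never exceeds OS. Deaths, and progressions found at visits or on unscheduled scans, keep their actual dates. Read the curve at the nominal time, with events at that time included: week 54 from first nivolumab, or week 52 from radiation start. If radiation start is chosen, add a rule for events between first nivolumab and radiation.
3. Report as sensitivity analyses the 12-month Kaplan-Meier estimate with actual dates and an interval-censored 1-year PFS.

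In simulation at true 40%, this gives 38.7 to 38.8% at week 54 against a true 0.40^(378/365.25) = 38.7%, and 40.1 to 40.2% at week 52 from radiation against a true 40.1%. The upward bias is gone on both clocks.

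The cost is wording, plus one real downside. On the first-nivolumab clock the landmark moves about two weeks past 12 months, so under a constant hazard the 40% and 55% benchmarks become about 38.7% and 53.9%. State these beside the estimate. The rule also treats a late scheduled scan differently from a visit on the same day, which is a reason to report the actual-date analysis. Scans, visits and sample size do not change.
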